6.2. Study Procedures

6.2.1. Screening (Day -14)

All patients must provide written informed consent before any study specific assessments or procedures are performed. A subject enrollment form documenting the investigator's assessment of each screened subject with regard to the protocol's inclusion and exclusion criteria has to be completed by the investigator.

Based on the results of Visit 1 assessments (see below 'Screening Assessments at Visit 1'), potentially eligible patients will enter a wash-out period as necessary. Blood test data generated by the study site or central laboratory 3 days prior to Visit 1 can be accepted.

Screening Assessments at Visit 1

- Demographics, medical history, including previous and concomitant diseases and treatments
- Physical examination
- Anthropometric measures (Height, Weight, Waist circumference, BMI)
- Vital signs (pulse rate, body temperature, respiratory rate, and blood pressure)
- Urine Pregnancy Test
- Blood samples for
 - lipid profile (total cholesterol, TG, HDL-C, LDL-C and LDL/HDL ratio)
 - biochemistry (serum creatinine for estimating GFR)

Patients will be instructed to come in fasted state for all subsequent study visits. Patients should receive information on a heart healthy diet and counseling on lifestyle changes as appropriate.

6.2.2. Enrollment/Randomization (Day 1)

Randomization Assessments at Visit 2

Once a patient has fulfilled the entry criteria, he/she will be randomized into either Antroquinonol 150 mg, Antroquinonol 100 mg, Antroquinonol 50 mg or placebo treatment group using a permuted block randomization method with 1: 1: 1: 1 ratio. The subject will be registered with a randomization number, and the study drug will be administered. The importance of compliance with study drug should be emphasized.

The assessments listed below will be performed. If the eligibility is confirmed and a wash-out period is not needed for the subject, based on investigator's judgements, the blood test, CT Scan, and Doppler color flow mapping required at visit 2 can be replaced by data obtained 14 days before V2.

- Physical examination
- Anthropometric measures (Height, weight, waist circumference, BMI)
- Vital signs (pulse rate, body temperature, respiratory rate, and blood pressure)

- Blood samples for
 - lipid profile (total cholesterol, TG, HDL-C, LDL-C and HDL-C /LDL-C ratio)
 - hematology (WBC, RBC, Hb, Hct, RDW, platelet, MCV, MCH, MCHC, neutrophil-band and segment, lymphocyte, monocyte, eosinophil, basophil)
 - serum chemistry (AST, ALT, CPK, BUN, serum creatinine, albumin, total bilirubin, direct bilirubin, ALP, total protein)
 - biomarkers (hsCRP, IL-1, IL-6, and TNF-alpha)
- 12-lead electrocardiogram
- Brachial-ankle pulse wave velocity (baPWV) and ankle-brachial index (ABI)
- Doppler color flow mapping, and CT scan of the liver
- Urinalysis
 - routine urine test (pH, protein, glucose, ketone, blood, urobilinogen, bilirubin, nitrite, leukocyte)
 - clinical microscopy

In addition, information on adverse events during the wash-out period and new concomitant medications will be collected.

6.2.3. On treatment visits (Day 29±3, Day 57±3, Day 85±3)

During the treatment period, subjects will visit the clinic every 4 weeks. Subjects have to come in fasted state for all visits. Therefore, subjects will be instructed not to take study drug in the morning of study visits but to wait until all study assessments have been completed. Subjects will receive new drug supply at each visit and will be required to bring in all unused study drugs for assessment of compliance.

Treatment Period Assessments at Visit 3 and 4 (± 3 days)

The following evaluations will be performed at each visit throughout treatment:

- Physical examination
- Anthropometric measures (Height, weight, waist circumference, BMI)
- Vital signs (pulse rate, body temperature, respiratory rate, and blood pressure)
- Blood samples for
 - lipid profile (total cholesterol, TG, HDL-C, LDL-C and LDL/HDL ratio)
 - serum chemistry (AST, ALT, CPK, BUN, serum creatinine)
- Information on adverse events
- Information on new concomitant medications
- Record of drug dispense and drug return

End of Treatment Assessments at Visit 5 (± 3 days)

The following evaluations will be performed:

- Physical examination
- Anthropometric measures (Height, weight, waist circumference, BMI)
- Vital signs (pulse rate, body temperature, respiratory rate, and blood pressure)
- Blood samples for
 - lipid profile (total cholesterol, TG, HDL-C, LDL-C and LDL/HDL ratio)
 - hematology (WBC, RBC, Hb, Hct, RDW, platelet, MCV, MCH, MCHC, neutrophil-band and segment, lymphocyte, monocyte, eosinophil, basophil)
 - serum chemistry (AST, ALT, CPK, BUN, serum creatinine, albumin, total bilirubin, direct bilirubin, ALP, total protein)
 - biomarkers (hsCRP, IL-1, IL-6, and TNF-alpha)
- 12-lead electrocardiogram
- Brachial-ankle pulse wave velocity (baPWV) and ankle-brachial index (ABI)
- Doppler color flow mapping, and CT scan of the liver for patients with confirmed fatty liver at Visit 2
- Urinalysis
 - routine urine test (pH, protein, glucose, ketone, blood, urobilinogen, bilirubin, nitrite, leukocyte)
 - clinical microscopy
- Information on adverse events
- Information on new concomitant medications
- Record of drug return

6.2.4. Final study visit (Day 99±3)

Safety Follow-Up Assessments at Visit 6 (± 3 days)

A safety follow-up for all patients will be conducted 2 weeks after the end of treatment visit.

The following assessments will be performed:

- Physical examination
- Anthropometric measures (Height, weight, waist circumference, BMI)
- Vital signs (pulse rate, body temperature, respiratory rate, and blood pressure)
- Blood samples for
 - lipid profile (total cholesterol, TG, HDL-C, LDL-C and LDL/HDL ratio)
 - hematology (WBC, RBC, Hb, Hct, RDW, platelet, MCV, MCH, MCHC, neutrophil-band and segment, lymphocyte, monocyte, eosinophil, basophil)
 - serum chemistry (AST, ALT, CPK, BUN, serum creatinine, albumin, total bilirubin, direct bilirubin, ALP, total protein)

- biomarkers (hsCRP, IL-1, IL-6, and TNF-alpha)
- Urinalysis
 - routine urine test (pH, protein, glucose, ketone, blood, urobilinogen, bilirubin, nitrite, leukocyte)
 - clinical microscopy
- Information on adverse events
- Information on new concomitant medications
- Provide final instructions to subject

6.2.5. Early termination visit /Withdrawal visit

For subjects who prematurely withdraw from treatment, the same procedures as the one at the end of the treatment will be applied. An end of treatment visit should be scheduled as soon as possible and the assessments listed below should be performed. Subjects will be required to bring in all study drugs for assessment of compliance. If the decision of discontinuation is being taken while the subject is in the clinic for a visit, the end of treatment assessments may be performed on that day.

- Physical examination
- Anthropometric measures (Height, weight, waist circumference, BMI)
- Vital signs (pulse rate, body temperature, respiratory rate, and blood pressure)
- Blood samples for
 - lipid profile (total cholesterol, TG, HDL-C, LDL-C and LDL/HDL ratio)
 - hematology (WBC, RBC, Hb, Hct, RDW, platelet, MCV, MCH, MCHC, neutrophil-band and segment, lymphocyte, monocyte, eosinophil, basophil)
 - serum chemistry (AST, ALT, CPK, BUN, serum creatinine, albumin, total bilirubin, direct bilirubin, ALP, total protein)
 - biomarkers (hsCRP, IL-1, IL-6, and TNF-alpha)
- 12-lead electrocardiogram
- Brachial-ankle pulse wave velocity (baPWV) and ankle-brachial index (ABI)
- CT scan of the liver for patients with confirmed fatty liver at Visit 2
- Urinalysis
 - routine urine test (pH, protein, glucose, ketone, blood, urobilinogen, bilirubin, nitrite, leukocyte)
 - clinical microscopy
- Information on adverse events
- Information on new concomitant medications

A safety follow-up should be conducted for subjects who prematurely withdraw from treatment

2 weeks after the end of treatment visit. A clinic visit is recommended unless the subject refused to return. If so, the safety follow-up may be conducted via telephone.

Subjects willing to provide information should be followed for assessments of adverse events until the end of the trial. At a minimum, the investigator should make every effort to obtain information on whether or not the subject is alive or dead at the end of the study.

6.2.6. Unscheduled Visit

An unscheduled visit may be performed at any time during the study at the subject's request or as deemed necessary by the site investigator. The date and reason for the unscheduled visit will be recorded in the source documentation and CRFs. Following procedures/assessments will be performed at unscheduled visits if applicable:

- Physical examination
- Anthropometric measures (Height, weight, waist circumference, BMI)
- Vital signs (pulse rate, body temperature, respiratory rate, and blood pressure)
- Blood samples for
 - lipid profile (total cholesterol, TG, HDL-C, LDL-C and LDL/HDL ratio)
 - serum chemistry (AST, ALT, CPK, BUN, serum creatinine, albumin, total bilirubin, direct bilirubin, ALP, total protein)
- 12-lead electrocardiogram
- Information on adverse events
- Information on new concomitant medications

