7. WBC, RBC, Hb, Hct, RDW, platelet, MCV, MCH, MCHC, neutrophil-band and segment, lymphocyte, monocyte, eosinophil, and basophil.
8. Biochemical exam: AST, ALT, CPK, BUN and serum creatinine: visit 2 to visit 6; albumin, total bilirubin, direct bilirubin, ALP, total protein: V2, V5 and V6. At screening visit, serum creatinine shall be run for estimating glomerular filtration rate (GFR) **and data obtained 3 days prior to V1 is unacceptable.**
9. Urinary exam: routine urine test (pH, protein, glucose, ketone, blood, urobilinogen, bilirubin, nitrite, leukocyte) and clinical microscopy.

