7.5. Laboratory Evaluations

7.5.1 Clinical laboratory evaluations

Laboratory tests (including hematology, biochemistry, and urinalysis) will be scheduled as below. The examination items are included in **Table 7- 1**.

Lipid Profile: Blood samples to assess total cholesterol, triglycerides, HDL-C, LDL-C, LDL/HDL ratio will be obtained from visit 1 to visit 5.

Hematology: Blood samples to assess WBC, RBC, Hb, Hct, RDW, platelet, MCV, MCH, MCHC, neutrophil-band and segment, lymphocyte, monocyte, eosinophil, basophil will be obtained at visit 2 and visit 5.

Serum Biochemistry: Blood samples to assess AST, ALT, CPK, BUN and serum creatinine will be obtained from visit 2 to visit 5, albumin, total bilirubin, direct bilirubin, ALP, total protein will be obtained at visit 2 and visit 5. At screening visit, serum creatinine shall be run for estimating glomerular filtration rate (GFR).

Urinalysis: Assessments of urine pH, protein, glucose, ketone, blood, urobilinogen, bilirubin, nitrite, leukocyte and clinical microscopy will be tested at visit 2 and visit 5.

Pregnancy Test: Urine HCG test will be performed at visit 1.

12-lead ECG: ECG will be performed in accordance with the standard procedures at the site at visit 2 and visit 5.

baPWV and ABI measurement: baPWV is used to assess arterial stiffness and will be

obtained using VP 1000 or VP 1000 plus (Omron) at visit 2 and visit 5/early termination visit. ABI is a surrogate marker of atherosclerosis and will be obtained using the same device at visit 2 and visit 5/early termination visit.

Echocardiography: Values for S', E', and A' will be measured and averaged over three consecutive cardiac cycles. A composite mean for each of these parameters is then formed by taking the average of the values from the septal, lateral, and inferior wall. The ratio of the transmitral Doppler E wave velocity and the composite mean of E' will then be used to calculate the E/E' ratio. E/E' ratio will be obtained at visit 2 and visit 5.

CT scan of the liver: Each participant will undergo non-enhanced liver computed tomography (CT) scans at visit 2. The Hounsfield Unit (HU) attenuation of liver on CT scans will be utilized for determination of fatty liver (L/S ratio <1.0 and liver attenuation <40HU). Subjects who are confirmed with fatty liver will undergo liver CT scans again at visit 5.

Table 7- 1 Laboratory tests planned to be performed

Hematology	Biochemistry	Urinalysis	Others

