## 9.5 Safety Analyses

For the safety assessments, the information of adverse events will be described in detail. Count and percentage will be tabulated for the number of patients with AEs, number of total AEs, number of patients with AEs associated to study dosing and intensity. Adverse events will be coded by the Medical Dictionary for Regulatory Activities (MedDRA®) adverse event dictionary. All the AEs will be categorized by each represented Preferred Terms (PT) and System Organ Class (SOC), which will be tabulated by body system with related incidence rates. The clinical laboratory tests and electrocardiogram tests will be analyzed to separate subjects into normal and abnormal categories, with number of subjects and percentage of subjects in each category, and McNemar's test or Fisher's exact test will then be applied to test the changes between each visit.

Protocol: GHLIP-2-001

Study Sponsor: Golden Biotechnology Corporation

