## 10.2 Clinical Laboratory Evaluations

Descriptive summaries (mean, SD, median, minimum, and maximum for each group with related 95% confidence interval.) of changes from baseline will be presented for clinical laboratory values by treatment for the Safety Population.

The number of patients with clinical laboratory values below, within, or above normal ranges, pre-procedure versus post-procedure will be tabulated for each test, for the Safety Population by treatment group. Pre- and post-procedure values will also be presented with an analysis of mean changes from baseline. Laboratory assessment results will be classified to normal or abnormal, and will be tabulated with related frequency and percentages. The shift tables of laboratory results will also be provided.

Laboratory values that are outside the normal range will also be flagged in the data listings, along with corresponding normal ranges. Any out-of-range values that are identified by the investigator as being clinically significant will also be shown in a data listing.

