### 14.4 Safety Data

Table 14.4.1.1 Summary of Vital Sign by Visit (Safety Population)

Table 14.4.1.2 Summary of Mean Change from Baseline in Vital Sign (Safety Population)

Table 14.4.2.1 Summary of of Physical Examinations (Normal/Abnormal) (Safety Population)

Table 14.4.2.2 Transition Table of Physical Examinations (Safety Population)

Table 14.4.3.1 Summary of baPWV, ABI, E/E', and HU (Safety Population)

Table 14.4.3.2 Summary of of 12-Lead ECG, baPWV, ABI, E/E', and HU (Normal/Abnormal) (Safety Population)

Table 14.4.3.3 Transition Table of 12-Lead ECG, baPWV, ABI, E/E', and HU after 12 Weeks (Safety Population)

Table 14.4.4.1 Summary of Laboratory Assessment-Lipid Profile (Safety Population)

Table 14.4.4.2 Summary of Laboratory Assessment-Serum Chemistry (Safety Population)

Table 14.4.4.3 Summary of Laboratory Assessment-Hematology (Safety Population)

Table 14.4.4.4 Summary of Laboratory Assessment-Biomarkers (Safety Population)

Table 14.4.4.5 Summary of Laboratory Assessment-Urinary Exam (Safety Population)

Table 14.4.5.1 Summary of Laboratory Assessment-Lipid Profile (Normal/Abnormal) (Safety Population)

Table 14.4.5.2 Summary of Laboratory Assessment-Serum Chemistry (Normal/Abnormal) (Safety Population)

Table 14.4.5.3 Summary of Laboratory Assessment-Hematology (Normal/Abnormal) (Safety Population)

Table 14.4.5.4 Summary of Laboratory Assessment-Biomarkers (Normal/Abnormal) (Safety Population)

Table 14.4.5.5 Summary of Laboratory Assessment-Urinary Exam (Normal/Abnormal) (Safety Population)

Table 14.4.5.6 Summary of Laboratory Assessment-Microscopy (Normal/Abnormal) (Safety Population)

Table 14.4.6.1 Transition Table of Laboratory Assessment-Lipid Profile (Safety Population)

Table 14.4.6.2 Transition Table of Laboratory Assessment-Serum Chemistry (Safety Population)

Table 14.4.6.3 Transition Table of Laboratory Assessment-Hematology after 12 Weeks (Safety Population)

Table 14.4.6.4 Transition Table of Laboratory Assessment-Biomarkers after 12 Weeks (Safety Population)

Table 14.4.6.5 Transition Table of Laboratory Assessment-Urinary Exam after 12 Weeks (Safety Population)

Table 14.4.6.6 Transition Table of Laboratory Assessment-Microscopy after 12 Weeks (Safety Population)

Table 14.4.7.1 Summary of Subject Compliance for the Study Drugs (Safety Population)

Table 14.4.8.1 Summary of Adverse Events by Treatment Groups (Safety Population)

Table 14.4.8.2 Summary of Adverse Events by MedDRA Coding (Safety Population)

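### The SAP does not say how chemistry and ECG results from unscheduled and early-termination visits enter the by-arm safety tables, and it plans no worst post-baseline summary

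*Protocol*

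**What the plan says.** **Collection.** Protocol 6.2.6 lets an unscheduled visit take place "at the subject's request or as deemed necessary by the site investigator". Its list of tests, headed "Following procedures/assessments will be performed at unscheduled visits if applicable", contains a full serum chemistry panel and a 12-lead ECG. Protocol 6.2.5 requires chemistry and an ECG when a subject stops treatment early.

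**Schedule.** The flow chart in Protocol 6.1 gives "AST, ALT, CPK, BUN and serum creatinine: visit 2 to visit 6". Protocol 7.5.1 states that "ECG will be performed in accordance with the standard procedures at the site at visit 2 and visit 5".

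**Analysis.** SAP 9.5 classes laboratory and ECG results as normal or abnormal and says that "McNemar's test or Fisher's exact test will then be applied to test the changes between each visit". SAP 10.2 tabulates values below, within or above the normal range, "pre-procedure versus post-procedure will be tabulated for each test, for the Safety Population by treatment group". SAP 10.3 compares the baseline ECG with ECGs taken after screening. In the list of planned tables (SAP 14.4), "Table 14.4.3.3 Transition Table of 12-Lead ECG" carries a Week 12 time point in its title; the serum chemistry transition table (14.4.6.2) carries none.

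**Values after stopping.** Protocol 9.5 censors values measured after early termination of study drug and imputes nothing for safety analyses. It does not limit the censoring to efficacy data.

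**The concern.** The SAP never mentions unscheduled visits and does not say where test results from an early-termination visit belong. The programmer must decide whether such a result is dropped, assigned to the nearest scheduled visit or counted as a post-baseline value. Under the first choice, a rise in ALT or CPK that has settled by the next visit disappears from the by-arm tables.

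These tests matter here. Protocol 1.2 names raised transaminases and rhabdomyolysis as safety concerns with existing lipid-lowering treatment and as part of the reason for seeking another type of agent. Protocol 3.4 makes muscle symptoms a safety endpoint. By-visit tables that miss transient peaks could understate a dose-related effect on liver enzymes or CPK. If the rule is not fixed before unblinding, a later worst-value table would have to be labelled as unplanned under SAP 2 and 6.2.

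**Working it through.** The plan states no figure on this point, so the check sets the texts side by side.

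1. **Could such results exist?** Yes. Protocol 6.2.6 (if applicable) and 6.2.5 both list chemistry and a 12-lead ECG.

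2. **Does the SAP place them?**
   - SAP 9.5 ("will then be applied to test the changes between each visit") neither limits the comparison to scheduled visits nor extends it to others.
   - SAP 10.2 does not define the post-procedure value by visit.
   - SAP 10.3 does not exclude unscheduled ECGs, but gives no rule for using them.
   - SAP 14.4 ties the ECG transition table to Week 12, so an ECG taken between visits has no column there. The chemistry transition table has no time point and leaves the matter open.
   - No worst or peak post-baseline summary appears in SAP 9.5, 10.2, 10.3 or 14.4.

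3. **What happens at stopping?** The early-termination visit normally follows the decision to stop. Read literally, Protocol 9.5 can censor its chemistry and ECG. SAP 7.3 does not repeat or narrow that rule, and SAP 12 declares no change from the protocol.

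4. **What other route exists?** Protocol 8.1 counts abnormal laboratory findings as adverse events. SAP 10.1.1 counts events by maximum intensity and arm and compares System Organ Class rates across arms with Fisher's exact test. SAP 10.1.2 tabulates events leading to withdrawal by arm. This route needs the investigator to record an event, and it carries a term and a grade, not the measured value.

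5. **How far apart are scheduled assessments?**
   - Chemistry on Days 1, 29, 57, 85 and 99: 29 − 1 = 28, 57 − 29 = 28, 85 − 57 = 28, 99 − 85 = 14 days. (Protocol 7.5.1 ends chemistry at Visit 5, which leaves the on-treatment gaps unchanged.)
   - ECG on Days 1 and 85: 85 − 1 = 84 days.

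6. **Illustration only.** Suppose an abnormality lasts d days and starts at a random time in a gap of g days. The chance that it is present at the next scheduled visit is d/g. The documents give no duration; 7 to 14 days is an assumption.
   - Chemistry: 7/28 = 25%; 14/28 = 50%.
   - ECG: 7/84 = 8%; 14/84 = 17%.

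   These figures describe visit spacing. They do not show how many results would be left out of the tables, because the documents give no rate of unscheduled visits, and no table can recover an abnormality that nobody sampled.

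**The case against.** Four stronger readings are tempting, and the documents do not support them.

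- A reader might infer that the SAP analyses scheduled visits only. It does not say so. SAP 9.5, 10.2 and 10.3 and the undated chemistry transition table are open. Among the chemistry and ECG items cited here, only the ECG transition table is clearly tied to Week 12.
- A reader might infer that these findings enter no comparison with placebo. The adverse-event route contradicts this. Protocol 8.1 requires all events to be documented, and to be reported when in doubt; Protocol 6.2.6 itself collects adverse events; and events reach by-arm summaries and a between-arm test.
- A reader might assume that unscheduled visits happen because a patient is unwell. The trigger is the subject's request or the investigator's judgement, and the tests are done only if applicable.
- A reader might take the complements of the figures above (50% to 75% for chemistry, 83% to 92% for ECG) as results lost. They are not, and early-termination tests could also catch some of these abnormalities.

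Two further points are fair. McNemar's test is a paired, within-group test, so scheduled values also receive little formal comparison with placebo. SAP 7.6 allows derived variables unrelated to the primary or key secondary endpoints to be added without amending the SAP, so a worst-value variable could be programmed later; but that permission does not commit anyone to produce it.

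What remains is that there is no rule for these results, no worst post-baseline display and no exemption of safety data from the censoring.

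**Conclusion.** The point holds as a gap in specification. A transient ALT, CPK or ECG abnormality seen between visits or at stopping may or may not reach the by-arm laboratory and ECG displays, depending on a choice that the SAP leaves open. Its only assured route to a by-arm summary is being recorded as an adverse event.

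The gap is clearest for ECG, which has one scheduled on-treatment assessment and a transition table fixed at Week 12. It is less certain for chemistry, where the wording could accommodate unscheduled results. For early stoppers it rests on reading the Protocol 9.5 censoring as covering safety data, which the text permits but does not state.

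The effect on the trial's safety conclusions cannot be sized from the documents, and the primary efficacy analysis is untouched. This is an inexpensive improvement to the safety plan.

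**What to change.** In SAP 9.5 and 10.2, before unblinding:

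- State that by-visit tables use scheduled visits only.
- Add, by arm, a table of shifts from baseline to the worst post-baseline value for AST, ALT, CPK, creatinine and bilirubin. Use all post-baseline results, including unscheduled and early-termination visits. The range categories already in SAP 10.2 could serve.
- For ECG, no parameter is named that would define a worst value. Tabulate by arm whether the patient had any post-baseline abnormal result, using the existing normal/abnormal classes and the same set of visits.
- State that the censoring in Protocol 9.5 does not apply to safety data, and record this in SAP 12.
- Present these tables descriptively, with the number of measurements per patient by arm. Formal contrasts of each dose with placebo are not advised, because the extra sampling is triggered by request or judgement.

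The cost is SAP wording and one or two tables from data already collected. The downside is that patients sampled more often have more chances of an extreme value; the measurement counts let a reader judge that.
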